### **Serious Adverse Event Reporting**

#### Investigator Reporting Responsibilities to the Sponsor

SAEs due to any cause, whether or not related to the study drug, must be reported to the Sponsor or designee within 24 hours of occurrence or when the Investigator becomes aware of the event. Report SAEs by fax, email, or telephone call to:

[name]  
Senior Director, Clinical Research and Development  
Kiniksa Pharmaceuticals Corp.  
[name]  
[name]  
[contact]  
Tel (after hours): [contact]  
Email: [[contact]](mailto:[contact])

If the Investigator reports a SAE by telephone, then a completed SAE report form must follow within 1 business day and is to include a full description of the event and sequelae in the format detailed in the SAE reporting form.

The event must also be recorded on the standard AE e-CRF. Preliminary reports of SAEs must be followed by detailed descriptions as soon as possible including clear and redacted photocopies of hospital case reports, consultant reports, lab reports, autopsy reports, and other documents when requested and applicable and if available.

### **Pregnancy**

Formal reproduction toxicology testing of KPL-716 has not yet been performed.

Female subjects of childbearing potential must therefore agree to use a highly effective and protocol approved contraceptive method ([Section 6.3](#)) for the duration of the study and until

16 weeks after last study drug administration under this protocol. Regular pregnancy tests will be performed for female subjects of childbearing potential, as defined in [Appendix 1](#).

Male subjects who have a female partner of childbearing potential must agree to use a highly effective and protocol approved contraceptive method ([Section 6.3](#)) for the duration of the study and until 16 weeks after last study drug administration under this protocol.

If a subject becomes pregnant while participating in the study, study drug dosing must be discontinued immediately.

A female subject must immediately inform the Investigator if she becomes pregnant during the study. A male subject must inform the Investigator if his female partner becomes pregnant during the study. Pregnancies occurring up to 16 weeks after last study drug administration must be reported to the Investigator. The Investigator must report all pregnancies to the Sponsor or designee immediately and no later than 24 hours of their first knowledge of the pregnancy. The Investigator should counsel the subject that it is unknown what effects study drug might have on a fetus. Monitoring of the subject should continue until conclusion of the pregnancy.

Instances of fetal death or congenital abnormality, if brought to the attention of the Investigator at any time after cessation of the study treatment and considered by the Investigator to be possibly related to the study treatment, must be reported to the Sponsor as an SAE.

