#### 4.1.2.2 Randomization and Dosing

A loading dose of KPL-716 720 mg (2x maintenance dose) or matching placebo will be administered via two (2) SC injections within 30 minutes on Day 1 by the Investigator or qualified designee at the study sites.

All subsequent doses of KPL-716 (360 mg maintenance dose) or matching placebo will be administered by the Investigator or qualified designee at the study sites via a single SC injection.

All procedures assigned to dosing days are performed prior to study drug administration. The following activities will take place prior to each maintenance dose:

- Review of concomitant medications, therapies and procedures
- Review of adverse events
- Review of subject compliance
- Vital signs (performed before and after dosing on each dosing day)
- Completion of Pruritus VAS, Sleep Loss VAS
- Blood collection for PK

The following activities will take place prior to maintenance dosing at designated study visits as outlined in [Appendix 1](#):

- Physical examination
- Collection of safety blood and urine samples

- Urine pregnancy test (if applicable); a serum pregnancy test will be performed if the urine pregnancy test is positive

- Completion of 5-D pruritus questionnaire
- Completion of quality of life questionnaire (DLQI and ItchyQoL)

Subjects will be observed for 3 hours after completion of the loading dose, for 2 hours after the first 2 maintenance doses and for 1 hour after all subsequent doses. Vital signs will be measured every hour during the observation period. The post-dose observation period duration may be modified based on emerging safety and tolerability data.

Adverse events and concomitant medications will be collected throughout the study. Subjects will continue to complete their daily questionnaire on pruritus (WI-NRS) and sleep until the EOS Visit. CIU subjects will continue to complete their daily UAS7 questionnaire (on itch and hives severity) until the EOS Visit.

In case of study drug discontinuation, subjects will continue to follow the schedule of activities for each visit minus study drug administration.

In case of study drug interruption or missed dosing visits, subjects will resume the schedule of activities in accordance with their study day. Study drug will be discontinued if more than three consecutive doses are withheld or missed.

In case of early withdrawal from the entire study, subjects will complete an EOS Visit.

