**14 APPENDICES**

**14.1 Appendix 1: Schedule of Activities**

**Table A Schedule of Activities**

Study Visits	Screening	Treatment Period									Follow-up Period				
Week (W)	W-4 to W0	Baseline	W1	W2	W3	W4	W5	W6	W7	W8	W10	W12	W14	W16	W18 (EOS)
Day (D)	D -28 to -1	D1	D8	D15	D22	D29	D36	D43	D50	D57	D71	D85	D99	D113	D127
Study Procedures	Windows (D)	0	±1	±2	±2	±2	±2	±2	±2	±2	±2	±2	±2	±2	±2
Informed consent	X														
Demographics	X														
Medical and surgical history	X	X													
Prior medications, therapies, procedures	X	X													
Eligibility Assessment	X	X													
Safety Assessments															
Physical examination 	X	X		X		X		X		X		X		X	X
Vital signs 	X	X	X	X	X	X	X	X	X	X	X	X	X	X	X
Body weight, height, BMI 	X	X								X					X
ECG (12-lead) 	X	X								X					X
Adverse Events Monitoring	From the Screening Visit through EOS Visit (Week 18)														
Concomitant meds/therapies/procedures monitoring	From the Screening Visit through EOS Visit (Week 18)														

Study Visits	Screening	Treatment Period									Follow-up Period				
Week (W)	W-4 to W0	Baseline	W1	W2	W3	W4	W5	W6	W7	W8	W10	W12	W14	W16	W18 (EOS)
Day (D)	D -28 to -1	D1	D8	D15	D22	D29	D36	D43	D50	D57	D71	D85	D99	D113	D127
Study Procedures	Windows (D)	0	±1	±2	±2	±2	±2	±2	±2	±2	±2	±2	±2	±2	±2
Subject Compliance assessment	From the Screening Visit through EOS Visit (Week 18)														
Laboratory Tests															
Clinical laboratory blood tests	X	X		X		X		X		X		X		X	X
Urinalysis	X	X				X				X		X		X	X
Pregnancy test 	X	X								X					X
Serology (HIV, HBV, HCV)	X														
Urine Drug Screen 	X														
Dosing															
Randomization		X													
Study drug administration 		X	X	X	X	X	X	X	X	X					
Study drug accountability		X	X	X	X	X	X	X	X	X					
Efficacy Measures															
Daily NRS Tool for assessment of pruritus and sleep	Completed daily from the Screening Visit through EOS Visit (Week 18)														
Pruritus VAS	X	X	X	X	X	X	X	X	X	X	X	X	X	X	X
Sleep Loss VAS	X	X	X	X	X	X	X	X	X	X	X	X	X	X	X
5-D Itch Scale	X	X		X		X		X		X	X	X	X	X	X

Study Visits	Screening	Treatment Period									Follow-up Period				
Week (W)	W-4 to W0	Baseline	W1	W2	W3	W4	W5	W6	W7	W8	W10	W12	W14	W16	W18 (EOS)
Day (D)	D -28 to -1	D1	D8	D15	D22	D29	D36	D43	D50	D57	D71	D85	D99	D113	D127
Study Procedures	Windows (D)	0	±1	±2	±2	±2	±2	±2	±2	±2	±2	±2	±2	±2	±2

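### Under the stated 8-dose regimen no pregnancy test is scheduled at any of the seven maintenance-dosing visits (Weeks 1 to 7), and Table A marks a ninth dose at Week 8

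*Protocol*

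**What the plan says.** On pregnancy, protocol Section 7.5.1 makes four relevant statements:

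- On what is known of the drug: "Formal reproduction toxicology testing of KPL-716 has not yet been performed".
- The stop rule: "If a subject becomes pregnant while participating in the study, study drug dosing must be discontinued immediately".
- On testing: "Regular pregnancy tests will be performed for female subjects of childbearing potential, as defined in" (the reference is to Appendix 1).
- On the subject's own duty: "A female subject must immediately inform the Investigator if she becomes pregnant during the study".

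Section 4.1.2.2 introduces a list with "The following activities will take place prior to maintenance dosing at designated study visits as outlined in" (again a reference to Appendix 1), and one item on it reads "Urine pregnancy test (if applicable); a serum pregnancy test will be performed if the urine pregnancy test is positive".

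The row "Pregnancy test 4" in Table A has marks at Screening, Day 1, Week 8 and Week 18, and SAP 17.1 has the same four. Footnote 4 makes every test after Screening a urine test, with a serum test if the urine test is positive. Footnote 6 puts all procedures before dosing on dosing days.

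On the regimen, Section 4.1 gives a loading dose and seven further weekly doses, Section 4.4 gives a total of 8, and the SAP Introduction calls Week 7 the last planned dosing. The dosing row in SAP 17.1 ends at Week 7. In Table A, the study drug administration row and the row "Study drug accountability" both run on to Week 8.

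**The concern.** An order to stop dosing at once works only if the pregnancy is known. From Week 1 to Week 7 that knowledge depends on the subject recognising and reporting the pregnancy, or on an unscheduled test. The Week 8 test arrives when, on the stated regimen, there is no dose left to withhold.

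The list in Section 4.1.2.2 provides for a urine test before maintenance dosing at designated visits, yet the schedule designates none from Week 1 to Week 7. At stake is avoidable dosing in an unrecognised early pregnancy, with a drug that has no reproduction toxicology. No endpoint, estimate, power or error rate is involved.

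The Week 8 marks are a separate inconsistency. Read literally, Table A instructs sites to give a ninth dose.

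**Working it through.** **Inputs.** Visit days from Table A: Day 1 = D1, W4 = D29, W7 = D50, W8 = D57, W18 = D127. Doses from Section 4.1: 720 mg loading, 360 mg weekly maintenance. Days are nominal; visit windows (±1 day at Week 1, ±2 days from Week 2) shift them slightly.

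**1. Dose count.** Text: 1 + 7 = 8 doses, D1 and W1 to W7. SAP 17.1: 8 marks. Table A: 9 marks, D1 and W1 to W8. Table A is the outlier.

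**2. Tests at maintenance-dosing visits.** Test visits {Screening, D1, W8, W18} and dosing visits {W1 to W7} have no visit in common: 0 of 7. If the ninth mark were followed, the Week 8 test would precede that one dose, and W1 to W7 would still have none.

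**3. Other items on the same list.** Table A gives each of the other visible items in Section 4.1.2.2 at least one visit from W1 to W7:

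| Item | Visits within W1 to W7 |
|---|---|
| Physical examination | W2, W4, W6 |
| Safety blood tests | W2, W4, W6 |
| Urinalysis | W4 |
| 5-D | W2, W4, W6 |
| DLQI, ItchyQoL | W4 |
| Pregnancy test | none |

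**4. Intervals.** Now: 57 − 1 = 56 days from the Day 1 test to the next; 57 − 50 = 7 days from last planned dose to that test. With a Week 4 test: 29 − 1 = 28 and 57 − 29 = 28 days. The 127 − 57 = 70 days from W8 to W18 follow dosing and do not change.

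**5. Dose that could be withheld.** Total planned: 720 + 7 × 360 = 3,240 mg. Given before the D29 dose: 720 + 3 × 360 = 1,800 mg (56%). At most withheld (W4 to W7): 4 × 360 = 1,440 mg (44%). This is a ceiling on dose given, not on exposure: Section 4.4 reports a half-life of 168 hours (7 days) after 360 mg SC, increasing with dose, so drug from the first 1,800 mg would still be clearing.

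**6. Coverage.** The documents do not say how soon after conception a urine test turns positive. Assume a lag L of 14 days, range 10 to 21. Conceptions not visible at the Day 1 test and occurring up to D50 span 50 − (1 − L) = 49 + L days. The Week 4 test detects those up to D(29 − L), which is (29 − L) − (1 − L) = 28 days whatever L is. It misses 50 − (29 − L) = 21 + L days.

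| L (days) | Window | Detected | Missed |
|---|---|---|---|
| 10 | 59 | 28 (47%) | 31 (53%) |
| 14 | 63 | 28 (44%) | 35 (56%) |
| 21 | 70 | 28 (40%) | 42 (60%) |

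These are shares of days. They equal shares of conceptions only if conception is equally likely on each day.

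**7. Blood volume (Appendix 3).** The stated pregnancy maximum is 4 samples of 3 mL, 12 mL. As only the Screening test is routinely serum, 4 is best read as 1 Screening sample plus a possible reflex serum test at each of the 3 urine visits. A fourth urine visit makes it 5 × 3 = 15 mL, and the totals go from 43 to 44 samples and from 354 to 357 mL.

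**The case against.** The best case against is that this is a preference. Sections 4.1.2.2 and 7.5.1 leave the choice of visits to Appendix 1, and Appendix 1 makes it. The stop rule applies however a pregnancy becomes known. The protocol's answer to the missing toxicology is prevention: highly effective contraception from Screening to 16 weeks after the last dose, a negative serum test at Screening and a negative urine test on Day 1, the duty to inform the Investigator, and adverse event review at weekly visits. All of this stands, and it is why severity is low. It does not replace a scheduled test, because none of these measures would show a pregnancy that the subject has not noticed after Day 1.

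Two practical objections also stand. An amendment needs IRB/IEC approval, so the cost is more than a dipstick. And all subjects had completed Week 7 dosing when the SAP was finalized, so nobody in this trial would benefit.

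A reader might infer that the protocol breaks its own promise of regular testing or its own pre-dose requirement. The documents do not support that, since both statements defer to Appendix 1. A reader might also infer from Table A that subjects received a ninth dose. The SAP states that Week 7 was the last planned dosing, and nothing in either document shows that a Week 8 dose was given.

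**Conclusion.** The point holds as two small matters. First, on the stated 8-dose regimen, 0 of 7 maintenance-dosing visits carry a pregnancy test. A Week 4 test is a cheap improvement, not the correction of a breach. Its benefit is bounded: at most 4 of 7 maintenance doses (1,440 of 3,240 mg), and detection over about 28 of 63 days (44%), with 56% missed (range 53% to 60%). The coverage figures rest on the assumed lag of 14 days (10 to 21). The documents give no basis for estimating how many subjects would be affected.

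Second, the Week 8 administration and accountability marks in Table A are wrong as written, because they conflict with Sections 4.1 and 4.4, the SAP Introduction and SAP 17.1.

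Overall severity is low.

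**What to change.** 1. Add a pre-dose urine pregnancy test at Week 4 for women of childbearing potential, in Table A and SAP 17.1. Week 4 is the only visit from Week 1 to Week 7 with urinalysis scheduled, so urine is already collected there. The result must be read before the dose; the documents do not say whether the urinalysis sample can be shared for this.
2. In Appendix 3, raise the pregnancy-test maximum from 4 to 5 samples (12 to 15 mL) and the totals to 44 samples and 357 mL, to allow for a reflex serum test.
3. Delete the Week 8 marks for study drug administration and accountability in Table A.

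The cost is one dipstick per woman of childbearing potential at an existing visit, an occasional serum test, and a protocol amendment with IRB/IEC approval. No extra staff or routine invasive procedure is needed. Because dosing in this trial was complete when the SAP was finalized, the change improves the protocol as designed or a later one that reuses this schedule.

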#### Investigator Reporting Responsibilities to IRB

Unanticipated problems posing risks to study subjects will be reported to the IRB/IEC per their institutional policy. Copies of each report and documentation of IRB/IEC notification and acknowledgement of receipt will be kept in the Investigator's study file.

#### Sponsor Reporting Responsibilities to Participating Investigators

It is the responsibility of the Sponsor or designee to immediately notify all participating Investigators of any AE associated with the use of the study drug that is both serious and unexpected, as well as any finding from tests in laboratory animals that suggest a significant risk for human subjects.

### **7.5.2 Clinical Laboratory Evaluations**

Blood and urine samples will be collected for clinical laboratory evaluations (including clinical chemistry, hematology, urinalysis, and serology) at the time points specified in [Appendix 2](#).

At the Screening Visit and at any time during the study at the discretion of the Investigator and in consultation with the Sponsor, if needed, subjects will be asked to provide urine samples for a drugs abuse screening.

For all female subjects of childbearing potential, the serum pregnancy test will be performed at the Screening Visit and the urine pregnancy test will be performed at the designated

timepoints in [Appendix 1](#). A serum pregnancy test will be performed if urine pregnancy is positive.

An Investigator will perform a clinical assessment of all clinical laboratory test results.

After Screening, any clinically significant abnormal findings should be reported as AEs.

### **7.5.3 Vital Signs**

Supine blood pressure (systolic and diastolic), pulse rate, respiratory rate, and body temperature will be assessed at every visit from the Screening Visit through the EOS Visit (Week 18) as outlined in [Appendix 1](#). Subjects must be supine for at least 5 minutes before blood pressure and pulse rate measurements.

Vital signs may also be performed at other times if judged to be clinically appropriate by the Investigator or if the ongoing review of the safety data suggests a more detailed assessment of vital signs is required. All measurements will be performed singly and may be repeated if outside the relevant clinical reference range. Additional vital sign assessments may be performed if clinically indicated, in the opinion of the Investigator.

### **7.5.4 12-Lead Electrocardiogram**

The 12-lead ECG recording will be performed at the designated time points as outlined [Appendix 1](#).

Resting 12-lead ECGs will be recorded after the subject has been supine and at rest for at least 5 minutes.

Single 12-lead ECGs will be repeated twice if either of the following criteria apply:

- QT interval corrected for heart rate using Fridericia's method (QTcF) interval >450 ms in men and >470 ms in women
- QTcF change from the baseline (pre-dose) is > 60 msec

Additional 12-lead ECGs may be performed at other times if judged to be clinically appropriate or if the ongoing review of the data suggests a more detailed assessment of ECGs is required. The Investigator or designee will perform a clinical assessment of each 12-lead ECG.

Any new clinically significant ECG abnormalities occurring during the study will be recorded as AEs.

### **7.5.5 Physical Examination**

A full physical examination or an abbreviated physical examination will be performed at the timepoints specified in [Appendix 1](#).

A full physical examination includes head/neck/thyroid, eyes/ears/nose/throat (HEENT), lymph nodes, skin, respiratory, cardiovascular, gastrointestinal, musculoskeletal, and

neurological exams. Breast, anorectal, and genital examinations will be performed only if medically indicated.

An abbreviated physical examination includes skin, cardiovascular, respiratory, and abdominal exams and as indicated based on subject's symptoms.

## **7.6 Committees**

### **7.6.1 Safety Review Committee (SRC)**

During KPL-716-C202, periodic reviews of safety and tolerability data will be conducted by a safety data review committee consisting of Investigators from active sites and a Sponsor physician representative. In addition, the Sponsor will review internally emerging safety and tolerability data periodically.

## **8 SAMPLE SIZE AND DATA ANALYSES**

### **8.1 Statistical Methods**

All statistical analyses will be performed using Statistical Analysis Software (SAS®) Version 9.4 or later. All clinical study data will be presented in subject data listings. Descriptive statistics will be presented for all endpoints and will include number of subjects (n), mean, standard deviation (SD), first quartile (Q1), median, third quartile (Q3), minimum and maximum for continuous variables, and frequency and percentage for categorical and ordinal variables. Unless otherwise specified, all tests will be two-tailed using pre-specified levels of significance. Statistical analyses of efficacy endpoints will be conducted separately for each cohort. Details will be specified in the Statistical Analysis Plan (SAP).

### **8.2 Handling of Dropouts and Missing Data**

Criteria for removal of subjects from therapy or assessments are explained in [Section 4.8](#). To the extent possible, attempts will be made to minimize the amount of missing data through measures planned in the study conduct. Details for handling missing values will be specified in the SAP.

### **8.3 Multiple Comparisons/Multiplicity**

No Multiplicity adjustment is planned.

### **8.4 Determination of Sample Size**

This is a double-blind study. Each cohort will be independently analyzed. A total of approximately 26 subjects will be randomized in each cohort. The first 12 subjects will be randomized to the KPL-716 and the placebo arms in a 3:1 randomization ratio. The rest of the 14 subjects will be randomized in a 1:1 randomization ratio. There will be approximately 16 subjects and 10 subjects randomized to the KPL-716 arm and the placebo arm respectively. Based on a two-sample t-test for the primary efficacy endpoint, change from baseline in weekly average of WI-NRS at Week 8, assumed mean changes of 4 for the KPL-716 arm and 1.5 for the placebo arm, a total sample size of 26 subjects per cohort will provide about 80% power to detect a 2.5-point mean difference with a standard deviation of 2.8, given a two-sided alpha of 0.2. Given the exploratory nature of this pilot study, the precision attained with the above cohort samples size is acceptable for early signal of efficacy assessments.

### **8.5 Analysis Populations**

#### **8.5.1 Modified Intent-to-Treat Analysis Set**

All randomized subjects who receive at least one (1) dose of KPL-716 or placebo and have at least one (1) post-baseline efficacy assessment in the double-blind Treatment Period will be included in the modified intent-to-treat (mITT) analysis set. Efficacy analyses will be based on the mITT analysis sets. All mITT analyses will be based on each subject's randomized treatment assignment.

### **8.5.2 Safety Analysis Set**

All randomized subjects who take at least one (1) dose of KPL-716 or placebo will be included in the Safety Analysis Set. Safety analyses will be based on the actual treatment (KPL-716 or Placebo) that was administered to each subject.

### **8.5.3 Per Protocol Analysis Set**

All mITT subjects who have no protocol deviations that may potentially bias statistical analyses of the study will be included in the PP set. Protocol deviations that may potentially bias statistical analyses will be defined in the SAP before database lock.

### **8.5.4 Pharmacokinetic Analysis Sets**

Subjects who received KPL-716 and who had at least one (1) PK sample will be included in the PK population.

## **8.6 Efficacy Analyses**

Efficacy endpoints are defined in Section 3. All efficacy analyses for each disease cohort will be done separately based on the mITT analysis set. The analyses of primary and selected secondary efficacy endpoints will be repeated using the PP set to assess the sensitivity of the results to deviations of the protocol that could potentially bias the analysis. All efficacy data will be listed by subject. Missing data will be imputed using the last observation carried forward (LOCF) method. The corresponding p-value and 80% CI for the treatment mean difference will be displayed. Sensitivity analyses will be conducted. Details for the analysis will be provided in the SAP.

